6.6.2. Subject Replacement

At the Sponsor's discretion, subjects who withdraw or are withdrawn before taking study drug may be replaced. Should greater than 10% of treated patients withdraw before the primary endpoint visit or miss the primary endpoint visit due to events that could not be foreseen during study design planning (e.g., COVID-19 pandemic) then treated subjects may be replaced. Safety data will be presented for all subjects in the Clinical Study Report (CSR) regardless of whether the subject was a replacement.

6.6.3. Study Discontinuation

The Sponsor reserves the right to discontinue these studies at any time for any reason.

Periodic reviews of accumulating data by the IDMC may lead to the committee's recommendation of pausing dosing or terminating the Studies. In the event of premature Study termination, best efforts to guarantee appropriate safety follow-up of subjects who have already been enrolled will be made and IRB/IEC/REBs and the Regulatory Authorities will be informed.

6.7. Pregnancy

If a female subject or the partner of a male subject becomes pregnant during the Study or within 7 days of the subject's last dose of Study drug, the Sponsor clinical Study director (or designee) must be notified immediately. If the female subject is still on Study drug treatment, the Study drug must be discontinued immediately. Follow-up information regarding the outcome of the pregnancy and any postnatal sequelae in the infant will be required.

All pregnancies whether by the subject participating in the Study or the female partner of the male subject in the Study should be reported within 24 hours of awareness using the Pregnancy Notification Form.

7. ADVERSE EVENTS

7.1. Definitions

The definitions below are based on International Conference on Harmonization (ICH) guideline E2A, “Clinical Safety Data Management: Definitions and Standards for Expedited Reporting”.

7.1.1. Adverse Events (AE)

An AE is any untoward medical occurrence in a patient or clinical trial subject administered a pharmaceutical product that does not necessarily have to have a causal relationship with this treatment. An AE can therefore be any unfavorable and unintended sign (including an abnormal laboratory finding), symptom, or disease temporally associated with the use of a medicinal product, whether or not related to the medicinal product.

- AEs may be new events
- Preexisting events that increase in frequency, severity or change in nature or seriousness during or as a consequence of participation in clinical studies.
- Pre- or post-treatment complications that occur as a result of a protocol-mandated procedure (such as a biopsy).
- AEs may be clinically significant changes from baseline in physical examination, laboratory tests, or other diagnostic investigation (e.g., laboratory results, x-ray findings).
- AEs may result from an overdose of the Study medication.

Whenever possible, the diagnosis (rather than a series of terms related to a diagnosis) should be recorded as the AE term.

An AE does not include the following:

- Medical or surgical procedures (such as surgery, endoscopy, tooth extraction, or transfusion); the condition that leads to the procedure is an adverse event
- Preexisting diseases or conditions present or detected before signing an informed consent form that do not worsen
- Situations where an untoward medical occurrence has not occurred (such as hospitalization for elective surgery or social and/or convenience admissions)
- Overdose of either Study drug or concomitant medication without any signs or symptoms, unless the subject is hospitalized for observation

Any medical condition or clinically significant laboratory abnormality with an onset date prior to the time the subject signed the informed consent form is considered to be preexisting and should be documented in the medical history CRF.

Pregnancy is not an AE; however, if a female subject becomes pregnant during the conduct of the Study, the sponsor, will be notified according to the procedures for SAE reporting as outlined

in Section 6.4.3. Follow-up information regarding the outcome of the pregnancy and any fetal or neonatal sequelae will be obtained and documented.

7.1.2. Serious Adverse Event (SAE)

A serious adverse event (SAE) is defined as any untoward medical occurrence occurring at any dose that results in any of the following outcomes:

- Death
- Life-threatening situation. “Life-threatening” refers to a situation in which the patient was at risk of death at the time of the event; it does not refer to an event which might have caused death if it were more severe.
- Inpatient hospitalization or prolongation of existing hospitalization
 - Note: “Inpatient hospitalization” means the subject has been formally admitted to a hospital for medical reasons, for any length of time. This may or may not be overnight. It does not include presentation and care within an emergency department. A scheduled hospitalization for a pre-existing condition that has not worsened during participation in the study does not meet this criterion. Pre-planned hospitalizations for an elective medical/surgical procedure, scheduled treatments, or routine check-ups do not meet this criterion. Complications that occur during hospitalizations are AEs. If a complication prolongs hospitalization, it is an SAE.
- Disability. A persistent or significant incapacity or substantial disruption to the ability to conduct normal life functions.
- Congenital anomaly/birth defect in the offspring of a subject who received Study drug
- Important medical events that may not result in death, be immediately life-threatening, or require hospitalization, may be considered an SAE when, based upon appropriate medical judgment, they may jeopardize the subject and may require medical or surgical intervention to prevent one of the outcomes listed in this definition. Examples of such events are as follows:
 - Intensive treatment in an emergency room or at home for allergic bronchospasm
 - Blood dyscrasias or convulsions that do not result in hospitalization
 - Development of drug dependency or drug abuse

7.1.3. Additional Considerations for Serious Adverse Events

- Death is an outcome of an adverse event and not an adverse event in itself. Deaths of unknown cause for which the investigator cannot identify a cause of death will be captured as death of unknown cause or death not otherwise specified.
- All deaths, regardless of cause, must be reported for subjects if the death occurs while the subject is participating in the Study.

- “Occurring at any dose” does not imply that the subject is receiving Study drug at the time of the event; dosing may have been given as treatment cycles or interrupted temporarily before the onset of the SAE but may have contributed to the event.

7.1.4. Adverse Events of Special Interest (AESI)

At each Study visit, the Investigator (or designee) will specifically query for any adverse events of special interest (AESI). The following events are considered AESIs for this Study:

- Suspected or confirmed intestinal perforation
- Complicated herpes zoster (multi-dermatomal, disseminated, or with ophthalmic or CNS involvement)
- Malignancy excluding non-melanoma skin cancer
- Non-melanoma skin cancer
- Serious infection (e.g., that requires hospitalization or intravenous antibiotics)
- Opportunistic infections
- Thromboembolic disease (e.g., DVT, pulmonary embolism)
- Clinical laboratory abnormalities of concern (Refer to Section 7.2)
- Major cardiovascular event (e.g., myocardial infarction or cerebrovascular accident)

All AESIs, except for non-melanoma skin cancers and mono-dermatomal herpes zoster, must be reported to TBPH Clinical Safety and Pharmacovigilance within 24 hours of the time the Investigator or his/her designee becomes aware of an AESI (Refer to Section 7.4.3). Except for non-melanoma skin cancer that has been fully resected, mono-dermatomal herpes zoster, and certain laboratory abnormalities that are deemed by the investigator to not place subjects at immediate safety risk, all of these AESI’s should lead to discontinuation of the study drug. For each of these AESI, an additional targeted questionnaire needs to be completed to assess for risk factors. For thromboembolic events in particular, the subject should undergo evaluation for hypercoagulable state (e.g., with clinically relevant investigations, such as referral to a specialist and/or blood testing for a predisposition to a hypercoagulable state) and repeat imaging to assess resolution of the finding.

Besides these AESI, for other AEs, study drug may be interrupted and resumed as deemed medically appropriate by the investigator (e.g. during an infection that requires oral antimicrobial treatment).

7.2. Clinical Laboratory Abnormalities and Other Abnormal Assessments as Adverse Events or Serious Adverse Events

Abnormal laboratory findings (such as clinical chemistry, hematology, or urinalysis) or other abnormal assessments (such as electrocardiograms [ECGs], X-rays, or vital signs) that are associated with signs and/or symptoms or are considered clinically significant in the judgment of the investigator must be recorded as AEs or SAEs if they meet the definition of an adverse event

(or serious adverse event), as described in Section 7.1.1 (Adverse Event) and Section 7.1.2 (Serious Adverse Event).

Clinical laboratory abnormalities of concern may include, but are not limited to, the following where the investigator must recheck within 2-7 days, except for AST or ALT > 3x ULN where these need to be rechecked within 48-72 hours, as deemed appropriate by the investigator:

- clinically significant reduction in neutrophils or leukocytes or lymphocytes that may place subjects at higher risk for infection such as:
 - moderate or severe neutropenia (e.g., absolute neutrophil count of $< 1.0 \times 10^9/L$)
 - moderate or severe leukopenia (e.g., white blood cell count of $< 2.0 \times 10^9/L$)
 - moderate or severe lymphocytopenia (e.g., absolute lymphocyte count of $< 0.5 \times 10^9/L$)
- abnormal hepatic panel (AST or ALT > 3x ULN)
- an excessive decrease in creatinine clearance (e.g., a reduction by $\geq 50\%$ from baseline (baseline for this purpose is defined as creatinine clearance calculated for Day 1, predose activities))

Depending on the subject's baseline and individual scenario, the investigator should report as an AESI and stop study drug treatment if any of the below is seen:

- moderate or severe neutropenia (e.g., absolute neutrophil count of $< 1.0 \times 10^9/L$) on two sequential laboratory reports
- moderate or severe leukopenia (e.g., white blood cell count of $< 2.0 \times 10^9/L$) on two sequential laboratory reports
- moderate or severe lymphocytopenia (e.g., absolute lymphocyte count of $< 0.5 \times 10^9/L$) on two sequential laboratory reports
- a reduction by $\geq 50\%$ from baseline in creatinine clearance on two sequential laboratory reports
- Abnormal AST or ALT > 3x ULN on two sequential laboratory reports with bilirubin > 2x ULN on at least one of the two laboratory reports or international normalized ratio (INR) > 1.5 on at least one of the two reports (INR will be checked locally)
- AST or ALT > 5x ULN on two sequential laboratory reports at least 2 weeks apart
- AST or ALT > 3x ULN associated with signs or symptoms suggestive of acute liver injury (e.g., the appearance of fatigue, nausea, vomiting, right upper quadrant pain or tenderness, fever, rash, and/or eosinophilia [$> 5\%$])
- AST or ALT > 8x ULN on one laboratory report

Note: See [Appendix 10](#) for an algorithm of evaluating and managing subjects with ALT or AST > 3x ULN.

Merely repeating an abnormal test does not constitute an adverse event. Any abnormal test result that is determined to be an error does not require reporting as an adverse event.

If there are any AE questions, the investigator is encouraged to contact the Sponsor to discuss.

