6.6. Discontinuation

6.6.1. Subject Discontinuation

Any subject may withdraw their consent to participate in the Study at any time without prejudice. The investigator must withdraw from the Study any subject who requests to be withdrawn. A subject's participation in the Study may be discontinued at any time at the discretion of the investigator and in accordance with his or her clinical judgment. Subjects must also be discontinued on study drug for any AESI (except non-melanoma skin cancer, mono-dermatomal

herpes zoster, and certain laboratory abnormalities that are deemed by the investigator to not place subjects at immediate safety risk) or if the subject becomes pregnant. When possible, the tests and evaluations listed for the termination visit should be carried out. If a subject withdraws before completing the Study, the reason for withdrawal is to be documented on the CRF.

The Sponsor will be notified of all subject withdrawals.

Reasons for which the investigator or the Sponsor may withdraw a subject from the Phase 2b/Phase 3 Induction Studies or Phase 3 Maintenance Study or a subject may choose to terminate participation before completion include the following:

- Adverse event
- Subject choice/Withdrawal of consent
- Major violation of the protocol
- Termination of the Study by the Sponsor
- Initiation of a prohibited medication ([Appendix 6](#)) for UC (except for rectal aminosalicylates and rectal corticosteroids during the clinical flare assessment)
- Lost to follow-up
- Pregnancy
- Colectomy

Subjects with laboratory abnormalities as outlined in Section 7.2 (i.e., two sequential occurrences of renal, leukocyte, leukocyte subset, or hepatic panel abnormalities or hepatic panel abnormalities with clinical sign or symptom of acute liver failure) should discontinue the study drug. Any non-laboratory-related AE considered an AESI defined in Section 7.1.4, except for non-melanoma skin cancer and mono-dermatomal herpes zoster, should also lead to study drug discontinuation. Subjects who discontinue Study drug early because of an adverse reaction should be encouraged to continue their participation in the follow-up safety assessments. If a subject fails to return for scheduled visits, a documented effort must be made to determine the reason.

Subject study completion is defined as completing the last study visit whether or not the subject discontinued study drug prematurely.

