3.1.3. Visit Windows

All assessments (including unscheduled assessments) will be summarized using analysis windows. The exception is the End of Study 4 week follow up visit which will not be windowed.

The terminology of unscheduled will be applied to assessments that are outside an analysis window regardless of the nominal label associated with the assessments in the EDC system.

The following visit windows will be used in the summary of clinical data.

Table 4: Visit Analysis Windows

Nominal Visit	Nominal Day	Start (days)	Stop (days)
Screening	NA	-28	-1
Day 1	1	1	1
Week 2	14	7	21
Week 4	28	22	35
Week 8a/8b	56	46	Minimum of: 
 • Day 71, or • 8 Week Induction period end date
Week 12	Extended Induction day 28	Extended Induction day 22	Extended Induction day 35
Week 16	Extended Induction day 56	Extended Induction day 46	Minimum of: 
 • Extended Induction day 71, or • Extended Induction period end date

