3.7.2.1. Adverse Events of Special Interest

An AE of special interest (AESI) is one of scientific and medical interest specific to understanding the investigational product and may require close monitoring and rapid communication by the investigator to the sponsor. The following are the AESI's defined for the study:

- Suspected or Confirmed Intestinal Perforation
- Complicated Herpes Zoster (multi-dermatomal, disseminated, or with ophthalmic or CNS involvement)
- Malignancy excluding non-melanoma skin cancer
- Non-melanoma skin cancer
- Serious Infection (e.g., that requires hospitalization or intravenous antibiotics)
- Opportunistic Infections
- Thromboembolic disease (e.g. deep vein thrombosis, pulmonary embolism)

- Clinical Laboratory Abnormalities of Concern
- Cardiovascular Event (e.g. myocardial infarction or cerebrovascular accident)

The incidence of AESI's will be summarized overall and by AESI category and preferred term.

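### Protocol 7.1.4 and 7.2 leave open which of two lists defines the laboratory AESI; separately, the Phase 2b threshold counts can lose an abnormal value to its own recheck

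*Protocol*

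**What the plan says.** Protocol 7.1.4 includes in its AESI list "Clinical laboratory abnormalities of concern (Refer to Section 7.2". It gives every AESI a 24-hour duty with no laboratory exemption: "All AESIs, except for non-melanoma skin cancers and mono-dermatomal herpes zoster, must be reported". For each AESI, "an additional targeted questionnaire needs to be completed to assess for risk factors". Its allowance for certain laboratory abnormalities that pose no immediate risk concerns stopping study drug only.

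Protocol 7.2 then has two lists. The first carries the AESI label: "Clinical laboratory abnormalities of concern may include, but are not limited to, the following where the investigator must recheck within 2-7 days", with 48-72 hours for AST or ALT above 3x ULN. The second does not carry the label. It says that, depending on the subject's baseline and situation, "the investigator should report as an AESI and stop study drug treatment if any of the below is seen".

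Protocol 6.6.1 summarises 7.2 for discontinuation as "two sequential occurrences of renal, leukocyte, leukocyte subset, or hepatic panel abnormalities", or hepatic abnormalities with clinical signs of acute liver failure.

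Both SAPs repeat the category name in 3.7.2.1 without criteria. In the Phase 2b SAP, AESIs "will be summarized overall and by AESI category and preferred term"; the Maintenance SAP tabulates them by SOC and preferred term.

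For laboratory tables, Phase 2b SAP 3.1.3 states: "All assessments (including unscheduled assessments) will be summarized using analysis windows". Section 3.1.4 makes laboratory results a special case: with several valid records in a window, the latest is used. Section 3.7.3.1 of each SAP counts subjects by timepoint for three thresholds: neutrophils, leukocytes and lymphocytes.

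**The concern.** An AESI category needs one meaning. Here the name points to one list and the instruction to report sits on another. Two sites with the same transient low neutrophil count, both recording it as an AE, could act differently. One would report within 24 hours and complete the questionnaire; the other would recheck and stop there. The Phase 2b AESI category row could then mix unconfirmed and confirmed findings.

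The laboratory threshold table would normally offset this, because it does not depend on what a site chooses to report. In Phase 2b, however, its record-selection rule works against the recheck that 7.2 requires, and the table does not cover hepatic or renal thresholds. Protocol 1.5 names white-cell, liver-test and creatinine changes among the effects seen with a systemic JAK inhibitor.

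**Working it through.** **1. The two lists in 7.2**

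| Finding | First list (recheck) | Second list (report as AESI and stop) |
|---|---|---|
| Neutrophils < 1.0, WBC < 2.0, lymphocytes < 0.5 (x 10^9/L) | one value | two sequential reports (3 criteria) |
| Creatinine clearance fall >= 50% | one value | two sequential reports (1) |
| AST/ALT > 3x ULN | one value | two sequential reports plus bilirubin > 2x ULN or INR > 1.5 (1); or with signs or symptoms of acute liver injury (1) |
| AST/ALT > 5x ULN | already covered by > 3x | two sequential reports at least 2 weeks apart (1) |
| AST/ALT > 8x ULN | already covered by > 3x | one report (1) |

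Criteria: 3 + 1 + 2 + 1 + 1 = 8. Needing two reports: 3 + 1 + 1 + 1 = 6. All eight fall inside the first list. The reverse fails: a single low neutrophil count, a single asymptomatic AST/ALT above 3x and up to 8x ULN, or a repeated isolated AST/ALT of 3-5x ULN is on the first list and meets none of the eight.

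**2. Which list governs**

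- Reading A: the first list is the AESI, and the second is the subset to report and stop. The shared name supports this. So does 7.1.4, which excuses some laboratory AESIs from stopping drug.
- Reading B: the second list is the AESI. It is the only place in 7.2 that speaks of AESI reporting, and the first list's stated duty is to recheck.
- Section 6.6.1 does not decide it. Read literally, it stops drug for two sequential hepatic abnormalities of any degree, which includes the repeated isolated 3-5x ULN case that the eight criteria leave out. It does not mention the single report above 8x ULN.

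**3. Recheck in the same Phase 2b window**

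Inputs: visit window of +/-3 days (Protocol Table 1); windows of days 7-21 for Week 2 and 22-35 for Week 4 (Phase 2b SAP Table 4); recheck lag of 2-7 days (7.2). Condition: draw day + lag <= window stop.

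- Week 2, draws on days 11-17, stop 21. Days 11-14: all 6 lags, 4 x 6 = 24. Days 15, 16, 17: 5 + 4 + 3 = 12. Total 36 of 7 x 6 = 42.
- Week 4, draws on days 25-31, stop 35. Days 25-28: 24. Days 29, 30, 31: 5 + 4 + 3 = 12. Total 36 of 42.
- Together: 72 of 84. At nominal days 14 and 28: 12 of 12.
- AST/ALT recheck at 2-3 days: 14 of 14 at each visit, 28 of 28. Adding an AST/ALT row without changing the count would therefore not be enough.

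Week 8a is left out because its window can end early at the first dose of the next period.

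**4. Thresholds not counted**

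Section 7.2 names five laboratory thresholds and each SAP counts three, omitting AST/ALT > 3x ULN and a creatinine clearance fall of >= 50%. CTCAE grading covers these two incompletely:

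- With an abnormal baseline, ALT grade 1 runs to 3.0 x baseline. From 1.5x ULN that is 1.5 x 3.0 = 4.5x ULN; from 1.9x ULN it is 1.9 x 3.0 = 5.7x ULN. Exclusion 20a sets the screening limit at 2x ULN.
- Cockcroft-Gault clearance is inverse in creatinine at fixed age and ideal body weight, so a 50% fall is a doubling. From 0.5x ULN it reaches 1.0x ULN, no grade; from 0.75x ULN it reaches 1.5x ULN, grade 1.

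The three counted thresholds fare better: each is grade 3 or worse, so the maximum-grade summary may still show a transient low count.

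**The case against.** The strongest reply is that a working rule exists and little depends on it. Section 7.1.4 sends the reader to 7.2, 7.2 says when to report an AESI, and investigators are encouraged to contact the sponsor with AE questions. Both lists leave room for judgement, and the question arises only for results recorded as AEs. That limits the weight of the point, but it does not supply the missing sentence.

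The backstops are also real:

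- In Phase 2b: listings of all results and of abnormal values, a listing of subjects with grade >= 2 values, shift tables, maximum CTCAE grade, and special-interest summaries for ALT, AST, bilirubin and creatinine.
- In Maintenance: a listing of abnormal values, shift tables and maximum grade.
- The readable part of Protocol Appendix 10 requires the medical monitor to be notified of hepatic abnormalities in that work-up, so sponsor awareness does not rest on the AESI label alone.

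These stand, which is why the point stays small. The Appendix 10 algorithm and the AESI report-form guidelines are not in the supplied text and may settle some hepatic cases.

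A reader might infer that the second list is plainly the definition and that 7.1.4 should simply cite it. The documents do not support that: Reading A also fits, and choosing the second list would take single asymptomatic AST/ALT values up to 8x ULN out of mandatory 24-hour AESI reporting. A reader might also infer that the recheck problem affects both SAPs. It does not. Maintenance SAP 3.1 summarises scheduled visits only, so a normal unscheduled recheck cannot displace a scheduled abnormal value.

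**Conclusion.** The point holds as a minor one, in two separate parts.

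First, the protocol does not say which 7.2 list defines the laboratory AESI, and 6.6.1 matches neither list fully on hepatic results. The consequence is uneven 24-hour reporting and questionnaires, and one descriptive Phase 2b category row whose content depends on how each site reads the text. Some variation would remain in any case because both lists allow judgement.

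Second, the Phase 2b rules as written let a normal recheck remove the abnormal value from the by-timepoint counts, and those counts omit two of five thresholds. The 72 of 84 figure counts calendar combinations and assumes draws within the +/-3-day window and rechecks at 2-7 days. It is not a share of subjects or of abnormal results, and the documents give no basis for a subject count. Nor is the value lost to the record: it stays in the listings. The CTCAE examples depend on an already raised ALT baseline or a low creatinine baseline.

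No efficacy analysis is affected.

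**What to change.** **(a) Laboratory threshold tables.** In Phase 2b SAP 3.7.3.1, add AST/ALT > 3x ULN and a creatinine clearance fall of >= 50% from baseline. For each of the five thresholds, count subjects with any post-baseline value meeting it, scheduled or unscheduled, alongside the by-timepoint counts. In the Maintenance table, add the same two rows. An any-value count there is optional: it would only add unscheduled abnormal values, and the recheck argument does not apply.

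**(b) Protocol wording.** Make 7.1.4 name the list in 7.2 that defines the laboratory AESI, with the sponsor confirming which one. Align the hepatic wording of 6.6.1 with that choice, and keep the investigator's discretion to report other results.

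The cost is a clarifying edit to two protocol sections, two table rows in each SAP and one extra count in Phase 2b. It needs no new data; the downside is a little extra programming.
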